9. STUDY DRUG MATERIALS AND MANAGEMENT

9.1. Study Drug

Please reference Section 8.1 for a description of the study drug.

9.2. **Restrictions**

9.2.1. Food and Fluid Intake

There are no dietary or food restrictions for this trial.

Increased fluid intake should occur before and after image acquisition to maintain proper hydration throughout the study period and decrease radiation exposure to the urinary bladder. To enhance imaging, subjects should be encouraged to void post study drug injection and prior to imaging.

Subjects should follow pre-imaging and preoperative guidelines as per institutional practices and in accordance with standard of care principles.

9.2.2. Activity

The radioactivity administered in this study is similar to other diagnostic radiopharmaceuticals and should be managed according to institutional policies.

9.3. Study Drug Packaging and Labeling

The final drug product (¹⁸F-DCFPyL) is a clear, colorless injectable solution at a strength of 5-75 mCi/mL (185-2775 MBq/mL) ¹⁸F-DCFPyL at End of Synthesis (EOS). ¹⁸F-DCFPyL will be dispensed and filled into a unit-dose syringe. The final drug product will be placed into a lead pig and delivered to the clinical site in shipping containers with lead shielding.

Labels will be generated according to local policies and meet minimum requirements for labeling radioactive materials in compliance with federal, state, and local pharmacy regulations. Progenics minimum requirements for the syringe label will include the following: subject identifier, product name, dispensing lot number, ordered dose, dispense date/time, dispensed activity and volume, and beyond use date (BUD). An auxiliary sticker reading "New Drug—Limited by Federal Law to Investigational Use" shall be affixed to the unit-dose container.

9.4. Study Drug Storage

The study drug should be maintained at room temperature within the received lead shield unitdose system until time of administration.

9.5. Study Drug Preparation

The final drug product is supplied to each institution on the day of administration in a unit-dose syringe with no additional preparation required. Institutional policies and standard operating procedures (SOPs) should be followed for receipt and appropriate radiation safety handling. Before and after each administration, measure the amount of radioactivity in the syringe using an appropriate dose calibrator. Apply decay correction if necessary and calculate the administered dose accordingly.

9.6. Administration

Please see the Imaging Manual for complete details including pre-and post-injection measurement of the ¹⁸F-DCPyL Injection dose syringe. Administration must occur by the labeled expiration time.

- 1. Place an intravenous catheter in an antecubital vein or an equivalent venous access.
- 2. Ensure patency of the line with a saline flush.
- 3. Inject a bolus of 9±1 mCi (333±37 MBq) of ¹⁸F-DCPyL into the IV line or equivalent venous access by slow push from the appropriately shielded syringe according to normal local practices.
- 4. Administer an intravenous flush (e.g., 5-10 ml sterile Sodium Chloride Injection, 0.9%), to ensure full delivery of the dose.

If dose extravasation is noticed during or after completion of the drug administration:

- 1. Try to aspirate as much extravasated drug as possible through the still-intact catheter.
- 2. Imaging should proceed unless contraindicated for safety reasons.
- 3. Examine the skin area for local toxicity before discharge, and instruct subject to contact site immediately if local symptoms at injection site do not improve or worsen.
- 4. Note the event as an Adverse Event in the CRF and notify the Sponsor within 24 hours.

9.7. Study Drug Accountability

In accordance with ICH and FDA requirements, the investigator and/or drug dispenser must at all times account for all study drug furnished to the institution and prepared for the patient, whether used or unused.

No study agent is to be used outside of this study. Accurate and adequate accountability records must be maintained by the radiopharmacy, hot lab or nuclear medicine department responsible for receipt and dispensation of study drug. Records should include at minimum:

- Dates of receipt, lot number and quantities received from Sponsor or designee;
- Dates, subject numbers, and amount dispensed for administration to specific subjects;
- If applicable, dates, lot numbers, and drug quantities destroyed.

The investigator is responsible for ensuring that study agents are administered only to subjects included in this study in accordance with the study protocol.

Throughout the study, drug accountability will be performed by appropriate Sponsor personnel and when appropriate, reconciliation will be performed.

9.8. Study Drug Handling and Disposal

¹⁸F-DCFPyL Injection is a radioactive drug and should be handled by personnel trained in the proper use and disposal of radiopharmaceuticals according to institutional policies and applicable regulations or guidance. When handling and administering ¹⁸F-DCFPyL Injection, follow aseptic procedures and use effective radiation shielding, and appropriate safety measures to minimize radiation exposure.

Empty or unused product should be decayed at the site according to institutional policies and applicable state and federal regulations. Record the use and/or decay of study agent on the Drug Accountability record.

10. ASSESSMENT OF EFFICACY

10.1. Image Acquisition

10.1.1. ¹⁸F-DCFPyL PET/CT (all cohorts)

¹⁸F-DCFPyL PET imaging will be performed on local PET/CT scanners with CT for correction of physical effects (e.g., attenuation, scatter) and anatomic localization.

At 1-2 hours post ¹⁸F-DCFPyL injection, the subject will be asked to void, and a whole body CT and PET scan will be acquired from the mid-thigh through the vertex of the skull. Parameters for PET/CT scanning can be found in the Imaging Manual.

10.1.2. Bone Scan (all cohorts)

A radionuclide bone scan (either ^{99m}Tc-MDP or ¹⁸F-NaF PET/CT, depending upon the site's standard of care) will be obtained at Screening if one has not been obtained within six weeks (Cohort A) or four weeks (Cohort B) prior to study drug injection. If conducted as part of Screening, ¹⁸F-NaF PET bone scans must be done at least five physical half-lives (10 hours) prior to ¹⁸F-DCFPyL injection. Bone scan images will be submitted to the independent central imaging core lab per instruction in the Imaging Manual for assessment.

10.1.3. CT or MRI (all cohorts)

A contrast-enhanced CT of the chest, abdomen and pelvis (or non-contrast CT chest with Gadolinium-enhanced MRI of the abdomen and pelvis for subjects who have a medical contraindication to iodinated contrast) will be obtained at Screening if not already obtained within 6 weeks (Cohort A) or 4 weeks (Cohort B) prior to study drug injection. If CT is conducted at Screening, IV iodinated contrast medium cannot be administered within 24 hours of study drug injection. High density oral contrast medium (oral water contrast is acceptable) cannot be administered within 5 days prior to study drug injection. Copies of baseline CT or MR images will be submitted to the independent central imaging core lab per instruction in the Imaging Manual for assessment.

10.1.4. Biopsy Guided Imaging (cohort B only)

In Cohort B, imaging used to guide biopsy (i.e., CT/MRI) will be collected and reviewed centrally to confirm the biopsy location in the area of interest. The instruction for capturing biopsy images and directions for submitting the images to the independent central imaging core lab will be found in the Image Guided Biopsy Manual.

10.2. Image Interpretation

An independent imaging core lab will receive and evaluate ¹⁸F-DCFPyL PET/CT baseline, conventional images, and imaging used to guide biopsy (i.e., CT, MRI). The processes for image acquisition, transmittal and interpretation are detailed in the Imaging Manual and Imaging Review Charter documents.

10.3. Prostatectomy and Lymphadenectomy

Within 28 days post-study drug injection, all subjects in Cohort A will undergo standard of care RP with PLND as detailed in the Surgical Manual. Extent of PLND will be captured in the eCRF.

Surgical staff will label all specimens removed during surgery to correlate with the specific anatomic location of removal, in accordance with the Surgical Manual.

Should a subject receive alternate or additional procedure(s) for prostate cancer after dosing, the procedure and corresponding histopathology data will be recorded in the eCRF.

10.4. Interventional Radiology

Up to two lesions (one bone and one soft-tissue lesion, wherever feasible) may be biopsied in cohort B, within 28 days following ¹⁸F-DCFPyL imaging. If more than one lesion is obtained, the interventional radiologist will identify the specimen to be evaluated for diagnostic assessment and statistical analysis. The lesions most preferred for biopsy will be those that are suspicious on all or most imaging modalities and are in the investigators judgement safe for biopsy. The final biopsy site will be decided in consultation with the Interventional Radiology service for feasibility. Details regarding the collection of imaging used to guide biopsy (e.g., X-ray, CT, MRI) and transmittal to the central imaging lab can be found in the Image Guided Biopsy Manual. Images will be reviewed centrally to confirm uptake of ¹⁸F-DCFPyL in the area of interest.

Should a subject receive alternate or additional procedure(s) for prostate cancer after dosing, the procedure and corresponding histopathology data will be recorded in the eCRF.

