8.4. Randomization and Blinding

This is an open-label, non-randomized study. Three independent readers from a central imaging core lab will be given access to ¹⁸F-DCFPyL PET/CT imaging, conventional imaging, and biopsy-guided imaging. The central readers will be blinded to all other clinical information and radiology assessments. Likewise, the Investigator is responsible for ensuring that local pathologists who generate the histopathology results for the primary endpoint remain blinded to all imaging results.

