12.5.2.2. Secondary Endpoints

The following secondary efficacy endpoint analyses will be generated on the evaluable set.

Point estimates and two-sided 95% CIs will be presented for the following secondary endpoints:

- PPV and NPV will be computed for the pelvic lymph node packets (one observation per subject for cohort A).
- Sensitivity of ¹⁸F-DCFPyL PET/CT imaging within sites of metastasis or local recurrence relative to histopathology (cohort B)
- PPV will be computed for the biopsies (one observation per subject for cohort B).

The normal approximation to the binomial distribution will be used for endpoints having one observation per subject. The null hypothesis will be rejected for each if the lower limit of the

95% CI exceeds 0.50 for at least 2 of the 3 central readers. Statistics will be computed for each of the three central imaging core lab independent readers.

Lesions per subject, as detected by ¹⁸F-DCFPyL PET/CT and conventional images will be summarized for each tissue type (bone, lymph nodes, soft tissue, and prostate gland) and each of the three central imaging core lab independent readers using evaluable subjects from both cohorts.

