#### 4. STUDY DESIGN

## 4.1. Summary of Study Design

This is an open-label, non-randomized, Phase 2/3, multi-center study designed to evaluate the safety and diagnostic performance of F-DCFPyL PET/CT imaging to determine the presence or absence of metastatic prostate cancer in subjects with high risk prostate cancer who were planned for radical prostatectomy with pelvic lymph node dissection (cohort A), and subjects with radiologic evidence of local recurrence or new or progressive metastatic disease (cohort B) who were biopsied if a positive lesion was found on the F-DCFPyL PET/CT scan. The physician has the option to change the planned protocol specified procedure (i.e., RP ePLND for Cohort A subjects and Biopsy for Cohort B subjects) for the subjects based on the F-DCFPyL PET/CT scan. The details of these changes will be collected on the CRF, and these subjects obviating the planned procedure will not be included in any of the primary or secondary endpoints.

Eligible subjects will be enrolled in a non-randomized, sequential manner, with competitive enrollment between study sites. Ten (10) study sites will be used in the U.S. and Canada.

[figure not shown]
Diagnostic performance characteristics of F-DCFPyL PET/CT imaging will be evaluated using histopathology as the truth standard. Three independent readers from a central imaging core lab will be given access to F-DCFPyL PET/CT imaging, conventional imaging, and biopsy-guided imaging. The central readers will be blinded to all other clinical information (i.e. pathology data) and radiology assessments. Likewise, local pathologists who generate the histopathology results for the primary endpoint are blinded to all imaging results.

A change in clinical management questionnaire will be filled out by an independent urologist who is not otherwise a participant of the study. To maintain the blind for imaging, a statistician who is independent from the PyL study team will generate subject listings. A combination of imaging and clinical data will then be posted to a share point site where the independent urologist will review these data and fill out the questionnaire based on the results he sees prior to PyL imaging and then again after PyL imaging. To keep things simple, only imaging data from reviewer 1 will be presented for this assessment to be performed.

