#### **5.5.7.2.** Biopsy

Sensitivity and PPV are defined from imaging results in subjects undergoing a biopsy confirmed by conventional imaging and histology obtained from this biopsy. This will be performed for Cohort B only.

Criteria for Positive PyL Imaging Result	Criteria for Biopsy and Positive Histology
Biopsied Lesion consistent with PSMA Positive uptake on the  F-DCFPyL PET/CT = yes	Pathology result=Positive for prostate cancer

If Cohort =B, imaging and histology are obtained for the biopsy, and the above criteria are not met (Biopsied Lesion consistent with PSMA Positive uptake on the F-DCFPyL PET/CT = no or pathology result = negative) then results = Negative for each respective endpoint.

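### Cohort B: when two lesions are biopsied, the specimen analysed is chosen at discretion after PET, which can raise apparent sensitivity (though not, by that route, PPV)

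*Protocol*

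**What the plan says.** Protocol 10.4 permits more than one biopsy per Cohort B subject: "Up to two lesions (one bone and one soft-tissue lesion, wherever feasible) may be biopsied in cohort B". Where this happens, "the interventional radiologist will identify the specimen to be evaluated for diagnostic assessment and statistical analysis". Neither the Protocol nor the SAP adds a selection rule, says whether the choice comes before or after the pathology report, or says what becomes of the other specimen.

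The analysis takes one result per subject. Protocol 12.5.2.2 states that "PPV will be computed for the biopsies (one observation per subject for cohort B"), and Table 7 in Protocol 12.3.1 counts subjects with evaluable biopsies, not lesions. SAP 5.5.7.2 says that "Sensitivity and PPV are defined from imaging results in subjects undergoing a biopsy confirmed by conventional imaging", and scores the biopsied lesion as PSMA-positive or not, with no provision for two lesions. SAP section 10, which lists departures from the Protocol, does not address the matter.

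On blinding, Protocol 8.4 names two groups. "The central readers will be blinded to all other clinical information and radiology assessments", and the investigator must ensure that "local pathologists who generate the histopathology results for the primary endpoint remain blinded to all imaging results". The interventional radiologist is in neither group.

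Two passages bear on whether PET is known at biopsy. Protocol 10.4 adds that "The lesions most preferred for biopsy will be those that are suspicious on all or most imaging modalities". SAP 4.1 describes Cohort B subjects as those "who were biopsied if a positive lesion was found on the" PET/CT scan.

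**The concern.** Sensitivity is the proportion of histology-positive specimens that PET calls positive. If the specimen counted for a subject is picked from two with the PET result in view, the index test influences which observation enters its own evaluation. A subject with one PET-positive and one PET-negative cancer lesion can be entered as a true positive when an impartial pick would give a false negative half the time.

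Cohort B sensitivity and PPV are that cohort's main diagnostic endpoints. Protocol 12.5.2.2 judges them against a lower 95% limit of 0.50, and Protocol 3.1 says the study is meant to support marketing approval. The published estimate should not rest on an undocumented choice.

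**Working it through.** The plan has no figure of its own to reproduce: Protocol 12.1 gives no power calculation for Cohort B, only about 115 subjects dosed.

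**Inputs.** From the documents: one or two biopsied lesions per subject (Protocol 10.4), one result per subject and the 0.50 lower-limit rule (Protocol 12.5.2.2). Not in the documents, so assumed: f = 10% to 50%, q = 0.7 to 0.9, and that the PET-positive lesion is always taken when the pair is discordant.

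**Step 1, sensitivity with independent cancer lesions.** A single or impartially chosen lesion is PET-positive with probability q. If the PET-positive one of two is preferred, the probability is 1 − (1 − q)² = q + q(1 − q). Over the cohort, apparent sensitivity = q + f × q × (1 − q).

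| True q | f = 10% | f = 25% | f = 50% |
|---|---|---|---|
| 0.70 | 0.721 | 0.753 | 0.805 |
| 0.80 | 0.816 | 0.840 | 0.880 |
| 0.90 | 0.909 | 0.923 | 0.945 |

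The rise runs from 0.10 × 0.90 × 0.10 = 0.009 to 0.50 × 0.70 × 0.30 = 0.105.

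**Step 2, correlated PET results.** If the PET results of a subject's two cancer lesions have correlation φ, the chance that both are negative is (1 − q)² + φq(1 − q). The rise becomes f × q × (1 − q) × (1 − φ). At φ = 0.5 (assumed) every increment above is halved, giving about 0.5 to 5 points.

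**Step 3, allowing cancer-free lesions.** Assume 75% of biopsied lesions contain cancer, with sensitivity 0.80 and specificity 0.80.
- P(PET-positive) for one lesion = 0.75 × 0.80 + 0.25 × 0.20 = 0.65.
- PPV = 0.60/0.65 = 0.923; 1 − NPV = 0.15/0.35 = 0.429.
- With f = 25%, P(analysed lesion PET-positive) = 0.75 × 0.65 + 0.25 × (1 − 0.35²) = 0.707.
- Apparent sensitivity = 0.923 × 0.707 / (0.923 × 0.707 + 0.429 × 0.293) = 0.839, close to the 0.840 from Step 1.

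**Step 4, PPV.** PPV already conditions on a positive PET. With independent lesions, the cancer status of a chosen PET-positive lesion depends only on its own PET result, so PPV stays at 0.923. Simulation of 2,000,000 subjects per scenario, all with two lesions (f = 100%, hence an upper end), agrees. With latent disease correlation of 0.5 between lesions, PPV falls slightly, to 0.913. Two other ways of choosing can raise it:
- Taking the lesion with higher uptake: 0.923 to 0.941 (independent) or 0.926 (correlation 0.5). Across the assumed scenarios the change is about 1 to 6 points with independence and about 0 to 2 points with correlation 0.5.
- Choosing after pathology is known: 0.923 to 0.957 or 0.937. Across scenarios, about 1 to 12 points.

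**Step 5, effect on the 0.50 rule.** Assume 60 histology-positive subjects. At an observed 0.70, the lower limit is 0.70 − 1.96 × √(0.70 × 0.30/60) = 0.584, which already passes. In the assumed range the selection changes the estimate, not the pass or fail. For scale, at q = 0.70 and f = 30% the rise is 0.063, against a standard error of √(0.21/80) = 0.051 with 80 histology-positive subjects or √(0.21/103) = 0.045 with 103 (both numbers assumed).

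**The case against.** The strongest reply is that the radiologist cannot set the classification. PET positivity comes from three central readers, evaluability requires a conventional image confirming the sampled location (Protocol 12.2.3, SAP 5.4.3), and location or uptake is reviewed centrally (Protocol 10.1.4 and 10.4). This is true, but it controls how the chosen specimen is read, not which specimen is chosen.

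A second reply is that lesions suspicious on most modalities are preferred for biopsy, so PET-positive lesions may predominate and discordant pairs be few. That stands: at q = 0.90 and f = 10% the rise is under 1 point. The Image Guided Biopsy Manual is also not among the documents and could hold a rule, although the Protocol describes it as covering image capture and transmittal. A rule that defines the analysed observation belongs in the Protocol or SAP in any case.

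Three stronger readings are tempting and should be resisted:
- A reader might infer that choosing the PET-avid lesion inflates PPV as well. Preferring a positive to a negative lesion does not (Step 4). PPV rises only by the two other routes, which the text neither describes nor excludes.
- A reader might infer that the radiologist is known to be unblinded. The documents are silent. Awareness of PET is probable from Protocol 10.4 and SAP 4.1, but the supportable statement is that blinding is not stated.
- A reader might infer that the choice is made with pathology in hand. The sentence in Protocol 10.4 reads more naturally as a decision at the time of the procedure, and Protocol 10.5 sends specimens to pathology at once. Later choice is merely not ruled out.

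**Conclusion.** The point holds for sensitivity. As written, the plan lets someone not stated to be blinded to PET, and probably aware of it, decide which of two specimens is counted. Under the assumed values this adds about 1 to 10 points to apparent Cohort B sensitivity with independent lesions, and less where the two lesions tend to share a PET result. The size rests on the unknown share of subjects with two biopsies and on the PET-positive lesion being consistently preferred.

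The scope is limited to secondary endpoints, and only to subjects with two biopsies. The Cohort A co-primary endpoints are unaffected. PET-related choice of which site to biopsy is a separate and probably larger influence on Cohort B sensitivity. This is a cheap improvement worth making, not a flaw in the trial's main test.

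**What to change.** Replace the discretionary choice in Protocol 10.4, and add the same rule to SAP 5.5.7.2:
- When two lesions are biopsied, analyse the one named as the biopsy target on conventional imaging before the PET scan. Inclusion criteria 6 and 8 in Protocol 7.1 already require a radiologic finding and a planned biopsy, so a target can be named then.
- If neither or both were named, choose by a fixed PET-independent rule, for example the larger lesion on conventional imaging or a random pick. Order of sampling is not a suitable tie-break, because it can be set with knowledge of PET.
- Record the analysed lesion in the eCRF before pathology is reported.
- Where central reads and pathology already exist for the second lesion, add a supportive analysis of all biopsied lesions with subject-clustered standard errors.

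The cost is one eCRF field and a little analysis work. The supportive analysis is confined to existing reads because SAP 5.5.7.2 provides for a single biopsied-lesion result, and reading more lesions would add reader time. Which lesions are biopsied does not change, so PET-driven selection of the biopsy site remains and should be reported as a limitation of Cohort B sensitivity.

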#### 5.5.8. Lesions Per Subject

The number of lesions detected on imaging categorized as bone, lymph nodes, soft tissue, and the prostate gland will be determined by each of the central imaging core lab independent readers. The sum of lesions per subject per tissue type and overall will be computed for each subject based on each reader's lesion count. This will be calculated from the F-DCFPyL PET/CT scan results as well as the conventional imaging results.

Bone	Soft Tissue	Lymph nodes	Prostate Gland
BN Skull	ST Brain	LN Cervical	ST Prostate Gland Left
BN Thorax	ST Neck	LN Supraclavicular	ST Prostate Gland Right
BN Spine	ST Lungs	LN Axillary	
BN Pelvis	ST Esophageal	LN Mediastinal	
BN Extremities	ST Liver	LN Hilar	
	ST Gall Bladder	LN Mesenteric	
	ST Spleen	LN Elbow	
	ST Pancreas	LN Popliteal	
	ST Adrenal	LN Peri-aortic/para-aortic	
	ST Kidney	LN Other, Non-Pelvic	
	ST Bladder	PLN Template Right	
	ST Prostate Bed	PLN Template Left	
	ST Seminal Vesicle	PLN Pre-Sacral	
	ST Skin	PLN Other, Pelvic	
	ST Muscle		
	ST Other		

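### Cohort B sensitivity is scored from a yes/no item about the biopsied lesion, by readers who have the biopsy images and with no stated read order, so it measures uptake at a known site and may be biased upward

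*Protocol*

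**What the plan says.** - **Definition of the Cohort B PET result.** SAP 5.5.7.2 scores it positive when the item "Biopsied Lesion consistent with PSMA Positive uptake on the" tracer scan is answered yes, and negative when it is answered no. Sensitivity and PPV are computed from this item for each reader (SAP 7.7.2).
- **What the readers see.** Protocol 8.4: "Three independent readers from a central imaging core lab will be given access to ¹⁸F-DCFPyL PET/CT imaging, conventional imaging, and biopsy-guided imaging". It continues: "The central readers will be blinded to all other clinical information and radiology assessments". SAP 4.1 gives pathology data as an example of what is withheld. The biopsied site is not withheld.
- **Purpose of the central review of biopsy images.** Protocol 10.1.4 says that this imaging "will be collected and reviewed centrally to confirm the biopsy location in the area of interest". Protocol 10.4 says: "Images will be reviewed centrally to confirm uptake of ¹⁸F-DCFPyL in the area of interest". Protocol 12.2.3 asks only for a conventional image that confirms where the sample came from.
- **The readers' own lesion data.** SAP 5.5.8: "The sum of lesions per subject per tissue type and overall will be computed for each subject based on each reader's lesion count". These counts feed the detection-rate endpoint, not Cohort B sensitivity.
- **Read procedures.** Protocol 10.2: "The processes for image acquisition, transmittal and interpretation are detailed in the Imaging Manual and Imaging Review Charter documents". Neither of those documents was available for this review.
- **Success rule.** Protocol 12.5.2.2 rejects the null for a Cohort B endpoint if the lower 95% limit exceeds 0.50 for at least two of three readers.

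**The concern.** The endpoint in Protocol 5.2 and SAP 3.2.2 is worded as sensitivity to detect cancer within sites of metastasis or local recurrence. The item in SAP 5.5.7.2 can be answered only by someone who knows which lesion was biopsied. A reader who did not mark that lesion on the PET could still answer yes once shown where the needle went, knowing that the site was suspicious enough to sample. Among histology-positive subjects, such a change turns a miss into a hit.

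At stake is what the Cohort B figure means. If it is reported as detection, it may exceed what the readers would have found unprompted. All three readers have the same biopsy images, so a two-of-three rule does not cancel a shared push in one direction.

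**Working it through.** **Step 1. Compare how the two cohorts are scored.**

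| | Cohort A (SAP 5.5.7.1) | Cohort B (SAP 5.5.7.2) |
|---|---|---|
| PET result built from | reader lesion counts and regional calls, matched to resected tissue | one yes/no item about the biopsied lesion |
| Needs knowledge of the sampled site to answer | no; matching to resected tissue is done in the derivation | yes |
| Uses the reader's own marks | yes | not stated |

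No reason is given for the difference. The Cohort A primary endpoints do not use the biopsy item.

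**Step 2. Compare the two purposes of the central review.** Section 10.1.4 confirms location and section 10.4 confirms uptake. The guidance images listed in 10.4 (X-ray, CT, MRI) do not themselves show the tracer, so confirming uptake means consulting the PET with the target known. Confirming location does not require this.

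**Step 3. Look for a safeguard.** Neither document states a read order, a lock on the PET read, or a rule that the item is answered from lesions already marked. The Imaging Review Charter may contain one.

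**Step 4. Illustrate the possible size.** The documents give no power calculation for Cohort B (about 115 dosed), so there is no figure to reproduce. Two inputs are assumed: the number of histology-positive subjects, taken as 80, and r, the share of unprompted misses that become positive once the site is known.

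- Reported sensitivity = s + r(1 − s), where s is the unprompted sensitivity.
- For s = 0.70: r = 0.1 gives 0.70 + 0.1 × 0.30 = 0.73, and r = 0.5 gives 0.70 + 0.5 × 0.30 = 0.85.
- Fewest positives that pass with 80 subjects: 49/80 = 0.6125, and 0.6125 − 1.96 × √(0.6125 × 0.3875/80) = 0.506, which exceeds 0.50. With 48/80 the limit is 0.493, which does not.

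Exact binomial chance that one reader reaches 49 of 80, with the reported sensitivity in parentheses:

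| Unprompted s | r = 0 | r = 0.10 | r = 0.25 | r = 0.50 |
|---|---|---|---|---|
| 0.50 | 2.8% (0.50) | 15.6% (0.55) | 63.9% (0.625) | 99.8% (0.75) |
| 0.60 | 45.8% (0.60) | 73.7% (0.64) | 96.4% (0.70) | about 100% (0.80) |
| 0.70 | 96.4% (0.70) | 99.2% (0.73) | about 100% (0.775) | about 100% (0.85) |
| 0.80 | about 100% (0.80) | about 100% (0.82) | about 100% (0.85) | about 100% (0.90) |

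These are chances for one reader, not for the two-of-three rule. The pass/fail effect is large only when unprompted sensitivity lies near the threshold. Above about 0.70 the rule is met in any case, and only the reported estimate moves.

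**The case against.** Several points on the other side stand.

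- **The Charter may already deal with this.** It may lock the PET read and have the item answered by matching the biopsy site to lesions already marked. In that case there is no bias from this source. A lock alone would not be enough, because the item as the SAP defines it need not draw on the locked marks.
- **The item is neutral.** No is an allowed answer and is scored negative, readers are blinded to pathology, and each reader is analysed separately. A reader of Protocol 10.4 might infer that the central readers are told to confirm uptake. The documents do not support that: the sentence is passive, is not addressed to the three readers, and differs from 10.1.4.
- **A site-directed measure is a legitimate choice.** The Cohort B objective (Protocol 4.2) concerns presence or absence of cancer within sites of disease, and entry requires a lesion on imaging. Asking about the sampled lesion keeps PET and histology on the same tissue. The endpoint is nevertheless worded as detection.
- **The formula allows only upward error.** A lesion-specific question could also turn a nearby mark into a no. If the prompt also acts at histology-negative sites, it lowers PPV, which is reported alongside. For example, with 80% positive biopsies, sensitivity 0.60, specificity 0.90 and r = 0.25 (all assumed), PPV falls from 0.48/0.50 = 0.96 to 0.56/0.625 = 0.896.
- **The consequence is limited.** The endpoint is secondary and unpowered. SAP 7.7.2 keeps the 0.5 null but does not repeat the two-of-three rule.

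**Conclusion.** The point holds as a risk that arises from a stated endpoint rule. Cohort B sensitivity, as SAP 5.5.7.2 defines it, is uptake at a disclosed biopsy site, and nothing in the protocol or SAP ties the answer to an unprompted read. Relative to detection, the likely direction of error is upward. Its size cannot be derived from the documents and could be zero.

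A reader might go further and conclude that Cohort B sensitivity is inflated. The documents do not show this: it depends on the unseen Charter, and every figure for r, for the number of histology-positive subjects and for unprompted sensitivity above is an assumption.

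Selection of the biopsy site is a separate route to high sensitivity and is not counted here (Protocol 10.4 prefers lesions suspicious on most modalities, and SAP 4.1 describes biopsy after a positive PET). This is an inexpensive improvement to a secondary endpoint and does not touch the Cohort A primary analysis.

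**What to change.** 1. Reconcile Protocol 10.4 with 10.1.4 and 12.2.3, so that the central review of biopsy images confirms the biopsy location only.
2. State in the SAP and the Imaging Review Charter that each reader's PET read, with lesion locations, is locked before the biopsy images are released.
3. In SAP 5.5.7.2, score the PET positive when a lesion marked in that locked read matches the biopsied lesion, and negative otherwise, using a pre-specified lesion-level location rule. The SAP 5.5.8 region counts are too coarse for this: a count for the whole spine or pelvis could score a different lesion as a hit, which would itself raise sensitivity. Report the prompted item beside it as supportive.
4. If the sponsor keeps the prompted item as the main definition, report the locked-read version beside it and describe the prompted result as uptake at the biopsied site, not as detection.

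Cost: the same readers and images, SAP and Charter wording, recorded lesion locations, and a matching rule with a stated tolerance. Reported sensitivity may be slightly lower. The change does not remove every cue, because the readers also have the conventional imaging, which may already show the suspicious lesion.
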